3 STUDY DESIGN

MS-SMART is a multicentre, multi-arm, double blind, placebo-controlled phase IIb randomised controlled trial. A total of 440 patients with SPMS, with an entry criteria of an EDSS score of 4.0-6.5 will be equally randomised to receive placebo or one of the three active agents (amiloride 5mg bd, riluzole 50mg bd and fluoxetine 20mg bd). Patients will be followed up for 96 weeks with outcomedata collected after 0, 24, 48 and 96 weeks (see flowchart below). That is, the duration of the trial for a trial participant is 96 weeks (a telephone assessment at week 100, 4 weeks post completion will be conducted). This is standard practice for phase II trials in SPMS.

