4.2 INCLUSION CRITERIA

- Confirmed diagnosis of SPMS. Steady progression rather than relapse must be the major cause of increasing disability in the preceding 2 years. Progression can be evident from either an increase of at least one point in EDSS or clinical documentation of increasing disability in patients notes
- EDSS 4.0-6.5
- Aged 25 to 65 inclusive
- Women and men with partners of childbearing potential must be using an appropriate method of contraception to avoid any unlikely teratogenic effects of the 3 drugs from time of consent, to 6 weeks after treatment inclusive
- Women must have a negative pregnancy test within 7 days prior to the baseline visit unless not of child bearing potential (e.g. have undergone a hysterectomy, bilateral tubal ligation or bilateral oophorectomy or they are postmenopausal)
- Willing and able to comply with the trial protocol (e.g. can tolerate MRI and fulfils the requirements for MRI, e.g. not fitted with pacemakers or permanent hearing aids) ability to understand and complete questionnaires
- Written informed consent

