5.5.3 Withdrawal of Study Participants

Trial participants are free to withdraw from the trial at any point or can be withdrawn by the investigator. If withdrawal occurs, the primary reason for withdrawal should be documented in the participant's Case Report Form (CRF). Trial participant withdrawals will not be replaced.

If a participant discontinues study drug this does not necessarily constitute withdrawal. In this case all attempts should be made to follow up the participant as per protocol and/or re-commencing treatment (if discontinuation was due to adverse events which have subsequently resolved. Refer to section 10). It is important that all patients (with the exception of those that are withdrawn from the trial) undertake the final MRI scan at 96 weeks.

The IDMC can request trial or trial arm suspension/termination, according to the terms of the IDMC charter, for example unacceptable adverse events.

Sponsor No.12/0219 v7 Page **37** of **73**

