Trial participants will be contacted by telephone to monitor for any AEs occurring within 30 days following completion of trial medication. AEs occurring in the follow up period are to be reported as outlined in section 10.

The patients will then exit the study and their usual best medical care will resume.

Unscheduled visits

Participants will be instructed to contact the local study team between scheduled visits should they suspect a relapse. The proforma shown in appendix 4 will be completed and recorded in the CRF. An unscheduled visit (either for or not for a relapse) can occur at the local study team's discretion and the following will be assessed and recorded: review of current medical and MS history physical examination vital signs safety bloods at PI discretion relapse assessment (as per appendix 4) concomitant medication adverse events

Missed visits

It is vital that participants attend all clinic visits as scheduled. In the event that a visit cannot be re-scheduled the following measures may be taken:

- Concomitant medication and adverse event assessment by telephone
- Questionnaires are due at Visit 7 and 9 and may be sent to the participant for completion (please note this does not apply to the baseline questionnaires. Baseline questionnaires must be completed in clinic)
- Visit 7 and 9 telephone EDSS assessment as outlined above

Please note that these measures apply to participants on treatment and those off treatment and in follow up.

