10.2 DETECTING AEs AND SAEs

All AEs will be recorded in the medical records from the time a participant signs the consent form to take part in the study until study exit (Week 100).

Participants will be asked about the occurrence of AEs/SAEs at every visit during the study. Open-ended and non-leading verbal questioning of the participant will be used to enquire about AE/SAE occurrence. Participants will also be asked if they have been admitted to hospital, had any accidents, used any new medicines or changed concomitant medication regimens. AE data is also available from information written by the participant on the participant diary (this is considered source data). If there is any doubt as to whether a clinical observation is an AE, the event will be recorded.

AEs and SAEs may also be identified by support departments e.g. laboratory values.

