10.3 RECORDING AEs AND SAEs

Collection, recording and reporting of adverse events (including serious and non-serious events and reactions) to the sponsor will be completed according to the sponsor's SOP(INV/S05).

When an AE/SAE occurs, it is the responsibility of the Investigator to review all documentation (e.g. hospital notes, laboratory and diagnostic reports) related to the event. The Investigator will then record all relevant information on the AE log in the CRF and on the SAE form (if the AE meets the criteria of serious). However, if the AE is non-serious (see section 10.1 for serious criteria definition) or MS related (see section 10.4.6.1 for MS expected adverse events) these will remain in the source data (Medical records and Participant diary cards) only. Information to be

Sponsor No.12/0219 v7 Page **57** of **73** collected includes dose, type of event, onset date, Investigator assessment of severity and causality, date of resolution as well as treatment required, investigations needed and outcome.

Clinically significant abnormalities in the results of objective tests (e.g. laboratory variables) will also be recorded as adverse events on the AE log in the CRF, and if are not expected as part of disease or IMP, these will be recorded as unexpected.

All adverse events will be recorded with clinical symptoms and accompanied with a simple, brief description of the event, including dates as appropriate.

All adverse events will be recorded until 4 weeks after the last clinical visit (study exit, visit 10) All Serious Adverse Events will be reportable to the sponsor up to 30 days post last IMP administration.

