Forced diuresis, dialysis, haemoperfusion, and exchange transfusion are unlikely to be of benefit. Activated charcoal, which may be used with sorbitol, may be as or more effective than emesis or lavage. In managing overdosage, consider the possibility of multiple drug involvement. An extended time for close medical observation may be needed in patients who have taken excessive quantities of a tricyclic antidepressant if they are also taking, or have recently taken, fluoxetine.

11. **PREGNANCY**

Pregnancy is not considered an AE or SAE; however, the Investigator will collect pregnancy information for any female participants or female partners of male participants who become pregnant while participating in the study.

Reporting to the sponsor will be completed as per the sponsor's SOP and using the UCL pregnancy notification forms (INV/S05). The Investigator will record the information on the sponsors Pregnancy Notification Form and fax this to the sponsor on [name] or preferably emailed to [contact], within 24 hours of being made aware of the pregnancy.

All pregnant female participants and partners of male participants will be followed up until following the outcome of the pregnancy.

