14.6 CONTINUATION OF DRUG FOLLOWING THE END OF STUDY

Trial medication will be discontinued after the final clinic assessment for each participant.

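### Pregnancy collection in section 11 ends about 2 weeks before the protocol's own 6-week post-treatment contraception period

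*Protocol*

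**What the plan says.** The relevant rules sit in separate sections of the protocol.

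- **Contraception (section 4.2, repeated in the synopsis).** Women, and men whose partners could conceive, must use contraception "from time of consent, to 6 weeks after treatment inclusive". The stated reason is possible, though unlikely, teratogenicity of the three drugs.
- **Pregnancy collection (section 11).** Pregnancy is not treated as an AE or SAE, but "the Investigator will collect pregnancy information for any female participants or female partners of male participants who become pregnant while participating in the study". A sponsor SOP, which is not shown, governs how notifications are sent. Known pregnancies are followed to outcome.
- **End of drug (section 14.6).** "Trial medication will be discontinued after the final clinic assessment for each participant". That visit is scheduled at week 96, with a window of up to 2 weeks late.
- **End of participation.** Section 3 states that "a telephone assessment at week 100, 4 weeks post completion will be conducted". After that call, section 7.2 says, "The patients will then exit the study and their usual best medical care will resume". Sections 10.2 and 10.3 also place study exit at week 100, or 4 weeks after the last clinic visit.
- **Early stoppers (section 5.5.3).** "If a participant discontinues study drug this does not necessarily constitute withdrawal", so a participant off drug can remain in follow-up to exit.

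**The concern.** The protocol chooses 6 weeks after treatment as the period in which conception should be avoided, but its collection rule is tied to being in the study, which ends about 4 weeks after the last dose. The two periods do not match, and nothing in section 11 links them.

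What is at stake is notification and outcome follow-up of a drug-exposed pregnancy conceived late in the period, including one with a normal or unknown outcome. If nobody is told of such a pregnancy, its outcome cannot be recovered afterwards. The primary analysis, sample size and error rate are not involved.

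**Working it through.** **Inputs from the protocol**

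- Contraception period after treatment: 6 weeks = 42 days (section 4.2).
- Last dose: week 96 = day 672 (sections 7.2 and 14.6).
- Study exit: call at week 100 = day 700, tolerance 4 days either way (sections 3, 7.2 and 10.2).

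**The protocol's own interval.** Exit minus last dose = 700 − 672 = 28 days, which reproduces the stated 4 weeks.

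**Uncovered days = 42 − (exit − last dose)**

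| Case | Exit − last dose (days) | Uncovered (days) |
|---|---|---|
| Last dose week 96, call day 700 | 28 | 14 (33% of 42) |
| Call 4 days early | 24 | 18 (43%) |
| Call 4 days late | 32 | 10 (24%) |
| Final visit week 98 (day 686), call 4 weeks later (day 714) | 28 | 14 |
| Final visit week 98, call kept at day 700 | 14 | 28 (24 to 32 with the tolerance) |
| Drug stopped by week 94, followed to week 100 | at least 42 | 0 |

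The first row is the base case. Section 3 also gives the duration per participant as 96 weeks. If participation were read as ending there, the gap would be the full 42 days, but sections 7.2 and 10.2 and the 100-week duration in the synopsis support week 100. A participant who withdraws from the trial while still on drug could also be uncovered for up to 42 days.

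**Do other rules close the gap?**

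- AE collection does not, because section 11 says pregnancy is not an AE or SAE.
- SAE reporting stops 30 days after the last dose (sections 10.3 and 10.5), which is itself 42 − 30 = 12 days short.
- Sections 10.5 and 10.6 keep SARs and SUSARs reportable later. That would catch a congenital anomaly only if someone learned of it and judged it drug-related.
- The last scheduled pregnancy test is at week 96, and section 7.2 describes the week-100 call as monitoring for AEs.
- Follow-up to outcome governs pregnancies already known. It does not lengthen the period in which a pregnancy must begin to be collected.

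**Expected number.** The protocol gives neither the number of participants or partners able to conceive nor a contraceptive failure rate. Assume 100 to 220 people and 1% to 5% failure per year:

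- Low: 100 × 0.01 × 14/365 = 0.04.
- High: 220 × 0.05 × 14/365 = 0.42.

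**The case against.** **No strict contradiction.** One rule governs participant behaviour and the other governs what the investigator collects, and both can be followed as written. That is correct. The point is a mismatch between the risk period the protocol chose and the period it records.

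**The sponsor SOP may set a longer period.** It may, and this cannot be checked. However, section 11 cites the SOP for reporting to the sponsor, while the limit on which pregnancies are collected is in the protocol sentence itself.

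**The 4-week limit is inferred.** Section 11 gives no stop date and does not define participation. This stands, but exit at week 100 is the best-supported reading, and the alternative of 96 weeks makes the gap larger.

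**The serious outcome is already covered.** A drug-related anomaly stays reportable after exit. That is true in principle, but it depends on someone hearing of a pregnancy that nobody was asked to notify.

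**Small and late.** Fewer than half a pregnancy is expected even at the high end, and 220 is half of all 440 participants although ages run to 65. This is version 7, dated June 2018. Recruitment is complete (section 1.2.2.1), and the overall trial period ends on 31 October 2018. An amendment now would help only participants not yet 6 weeks past their last dose. All of this stands and limits the importance of the point.

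**A question at week 100 precedes the uncovered days.** Also true: it can only prompt later self-report and cannot detect a conception that has not yet happened.

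**Conclusion.** The concern holds as a minor misalignment in safety collection. For participants who take drug to the final visit, 14 of the 42 post-treatment days (10 to 18 with the call tolerance) fall outside the pregnancy collection rule as written, and no other rule shown in the protocol reliably covers them. Participants who stopped drug by week 94 and stayed in follow-up to week 100 are not affected.

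The conclusion rests on reading participation as ending at the week-100 call, and on the unseen SOP not extending collection. The expected count of 0.04 to 0.42 pregnancies rests on inputs assumed here and applies to the whole trial, so what a change at this stage could recover is smaller still.

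**What to change.** In section 11, replace the limit to pregnancies arising during participation with a dated period: *from consent until 6 weeks after the last dose of study drug*. Tying it to the last dose matches section 4.2, covers late final visits and participants who withdraw while on drug, and removes the undefined term.

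At the closing call, ask participants to tell the site of any pregnancy conceived in that period, including one recognised after the call. Use the existing Pregnancy Notification Form and the existing follow-up to outcome.

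The cost is one sentence, one question at a call already scheduled, and an occasional notification reaching a site after exit. No visit, test or staff is added. The change would need the review set out in section 14.1: the chief investigator, the sponsor and the trials unit, plus ethics, regulatory and local R&D approval if the sponsor judges it substantial.

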12 TRIAL MANAGEMENT AND OVERSIGHT ARRANGEMENTS

12.1 TRIAL MANAGEMENT GROUP

The Central Trial Office is based in the Edinburgh Clinical Trials Unit (ECTU) and will provide support to each site. The office will be responsible for randomisation, collection of data in collaboration with the research nurses, data processing and analysis.

Publication and dissemination of the study results will be coordinated by ECTU in collaboration with the Chief Investigator and Investigators as per the publication policy.

The trial will be coordinated by a Project Management Group, consisting of the Chief Investigators, lead research staff from selected sites, selected grantholders, sponsor representatives and ECTU trial staff.

The Trial Manager will oversee the study and will be accountable to the Chief Investigator. The Trial Manager will be responsible for checking the CRFs for completeness, plausibility and consistency. Any queries will be resolved by the Investigator or delegated member of the trial team.

A Delegation Log will be prepared for each site, detailing the responsibilities of each member of staff working on the trial.

12.2 TRIAL STEERING COMMITTEE

A Trial Steering Committee (TSC) will be established to oversee the conduct and progress of the trial. The terms of reference of the Trial Steering Committee will be documented in a charter that will be held in the TMF at ECTU.

12.3 DATA MONITORING COMMITTEE

An independent Data Monitoring Committee (DMC) will be established to oversee the safety of participants in the trial. The terms of reference of the Data Monitoring Committee will be documented in a charter that will be held in the TMF at ECTU.

12.4 INSPECTION OF RECORDS

Investigators and institutions involved in the study will permit trial related monitoring and audits on behalf of the sponsor, REC review, and regulatory inspection(s). In the event of an audit or monitoring, the Investigator agrees to allow the representatives of the sponsor, REC and Regulatory Authority direct access to all study records and source documentation. In the event of regulatory inspection, the Investigator agrees to allow inspectors direct access to all study records and source documentation. In the event of an audit or monitoring and source documentation. Trial participants are informed of this during the informed consent discussion and participants will consent to provide access to their medical records.

Sponsor No.12/0219 v7 Page **63** of **73**

12.5 RISK ASSESSMENT

An independent risk assessment will also be carried out by the sponsor to determine monitoring requirement and if an audit should be performed before/during/after the study and if so, at what locations and at what frequency.

12.6 STUDY MONITORING

A Trial specific monitoring plan will be established for the trial in accordance with the sponsors SOPs. An appointed monitor will visit the Investigator site prior to the start of the study and during the course of the study and in accordance with the monitoring plan.

13 GOOD CLINICAL PRACTICE

The sponsor will ensure that the trial protocol, patient information sheet, consent form, GP letter and submitted supporting documents have been approved by the appropriate regulatory body (MHRA in UK) and a main research ethics committee, prior to any patient recruitment.

13.1 ETHICAL CONDUCT

The trial will be conducted in compliance with the protocol, the UK Regulations, EU GCP and applicable regulatory requirement(s).

A favorable ethical opinion will be obtained from the appropriate REC and local R&D approval will be obtained prior to commencement of the study.

Before a site can enrol patients into the trial, the Chief Investigator or designee must apply for NHS permission from their Trust Research & Development (R&D) and be granted written permission. It is the responsibility of the Chief Investigator or designee at each site to ensure that all subsequent amendments gain the necessary approval. This does not affect the individual clinician's responsibility to take immediate action if thought necessary to protect the health and interest of individual patients

An annual progress report (APR) will be submitted to the REC within 30 days of the anniversary date on which the favourable opinion was given, and annually until the trial is declared ended. The chief investigator and ECTU will prepare the APR.

13.2 REGULATORY COMPLIANCE

The study will not commence until a Clinical Trial Authorisation (CTA) is obtained from the appropriate Regulatory Authority. The protocol and study conduct will comply with the Medicines for Human Use (Clinical Trials) Regulations 2004, and any relevant amendments.

13.3 INVESTIGATOR RESPONSIBILITIES

The Investigator is responsible for the overall conduct of the study at the site and compliance with the protocol and any protocol amendments. As outlined in the principles of EU GCP, the following areas listed in this section are also the responsibility of the Investigator. Responsibilities may be delegated to an appropriate member of study site staff.

13.3.1 Informed Consent

The Investigator is responsible for ensuring informed consent is obtained before any protocol specific procedures are carried out. The decision of a participant to participate in clinical research is voluntary and should be based on a clear understanding of what is involved.

Sponsor No.12/0219 v7 Page **64** of **73**

Participants must receive adequate oral and written information – appropriate Participant Information and Informed Consent Forms will be provided. The oral explanation to the participant will be performed by the Investigator or qualified delegated person, and must cover all the elements specified in the Participant Information Sheet and Consent Form.

The participant must be given every opportunity to clarify any points they do not understand and, if necessary, ask for more information. The participant must be given sufficient time to consider the information provided. It should be emphasized that the participant may withdraw their consent to participate at any time without loss of benefits to which they otherwise would be entitled.

The participant will be informed and agree to their medical records being inspected by regulatory authorities and representatives of the sponsor(s) but understand that their name will not be disclosed outside the hospital.

The Investigator or delegated member of the trial team and the participant will sign and date the Informed Consent Form(s) to confirm that consent has been obtained. The participant will receive a copy of this document and a copy will be filed in the Investigator Site File (ISF) and participant's medical notes.

13.3.2 Study Site Staff

The Investigator must be familiar with the IMPs, protocol and the study requirements. It is the Investigator's responsibility to ensure that all staff assisting with the study are adequately informed about the IMPs, protocol and their trial related duties.

13.3.3 Data Recording

The Principle Investigator is responsible for the quality of the data recorded in the CRF at each Investigator Site. Any delegation of tasks must be clearly documented on the delegation log.

13.3.4 Investigator Documentation

Prior to beginning the study, each Investigator will be asked to provide particular essential documents to ECTU, including but not limited to:

- An original signed Investigator's Declaration (as part of the Clinical Trial Agreement documents);
- Curriculum vitae (CV) signed and dated by the Investigator indicating that it is accurate and current.

ECTU will ensure all other documents required by EU GCP are retained in a Trial Master File (TMF), where required, and that appropriate documentation is available in local ISFs.

13.3.5 GCP Training

All study staff must hold evidence of appropriate GCP training.

13.3.6 **Confidentiality**

All laboratory specimens, evaluation forms, reports, and other records must be identified in a manner designed to maintain participant confidentiality. All records must be kept in a secure storage area with limited access. Clinical information will not be released without the written permission of the participant. The Investigator and study site staff involved with this study may not disclose or use for any purpose other than performance of the study, any data, record, or other unpublished, confidential information disclosed to those individuals for the purpose of the study. Prior written agreement from the sponsor or its designee must be obtained for the disclosure of any said confidential information to other parties.

The Case Report Forms (CRFs) will not bear the subject's name or other personal identifiable data and only the subject's initials, date of birth and trial identification number, will be used for identification.

